## 2 INTRODUCTION

According to the GLOBOCAN estimates of cancer incidence and mortality, lung cancer has become the most commonly diagnosed cancer (11.6% of the total cases) and the leading cause of cancer death (18.4% of the total cancer deaths) worldwide[13]. Non-small cell lung cancer (NSCLC) represents approximately 80%-85% of all lung cancers. At the time of diagnosis, about 70% of NSCLC patients have locally advanced or metastatic disease who are not amenable to surgical resection. The 5-year overall survival rate for NSCLC patients with stage IV remains poor[14].

Fortunately, owing to the discovery of Epidermal Growth Factor Receptor (*EGFR*) pathway and the development of *EGFR*-targeted tyrosine kinase (TKI), the prognosis of advanced *EGFR* sensitive mutated (*EGFR*m+) NSCLC patients has improved significantly. The oncogenic *EGFR* mutation is present in 40-55% and 5-15% of lung adenocarcinoma cases in East Asia and in USA/European respectively[15]. The benefit of these *EGFR*-TKIs in *EGFR*m+ patients was initially demonstrated in the second-line and maintenance settings and subsequently confirmed in the first-line setting. As a result, the first- and second-generation *EGFR*-TKIs have been widely used in *EGFR*m+ NSCLC patients and brought improved ORR and PFS, but the benefit of overall survival is limited[16-18]. Based on the statistically significant improved PFS (18.9 months vs. 10.2 months; hazard ratio for disease progression or death, 0.46; 95% confidence interval [CI], 0.37 to 0.57; P<0.001) and OS (38.6 months vs. 31.8 months; hazard ratio for death, 0.80; 95.05% CI, 0.64 to 1.00; P = 0.046) from FLAURA study, the third-generation *EGFR*-TKI Osimertinib has become the new standard of care for advanced *EGFR* mutated NSCLC patients and has recommended as the preferred first-line treatment by NCCN guideline[1]. In China, Osimertinib has been approved as a first-line treatment for *EGFR* mutated advanced NSCLC in Aug 2019.

### 2.1 Study Rationale

The third-generation *EGFR*-TKI Osimertinib has been approved as first-line treatment for advanced *EGFR* mutated NSCLC in China, and has also been widely used in clinical practice no matter in the first-line or in the later-line. Prior reports of acquired resistance mechanisms to Osimertinib primarily focus on patients who received Osimertinib as the second-line treatment. Although some small sample studies have reported the possible resistance mechanisms of Osimertinib in the first-line treatment, it is still an urgent need to explore the whole gene profile in *EGFR*m advanced NSCLC patients post Osimertinib 1L treatment failure by paired tissue and plasma after disease progression following 1L Osimertinib to guide subsequent treatment strategy[6, 7].

MET overexpression is key resistance mechanism after 1L Osimertinib failure[8]. SAVANNAH observed improved outcomes in post 1L Osimertinib resistant *EGFR*m NSCLC

patients with MET IHC90+(≥90% tumour cells MET IHC3+) and/or FISH10+(MET copy number ≥10); the estimated prevalence of IHC90+ is 29% in SAVANNAH study published on 2022 WCLC [9]. MET amplification is also a key resistance mechanism after 1L Osimertinib failure[8].FISH is golden standard testing method for MET amplification. The prevalence of FISH 5+(MET copy number ≥5 and/or MET/CEP7≥2) in INSIGHT 2 study [10] is 33% and the prevalence of FISH10+ in SAVANNAH study is 20% [9]. The prevalence data of MET amplification by FISH testing and MET overexpression by IHC testing in Chinese advanced EGFRm NSCLC patients who had disease progression following 1L osimertinib are very limited and still need further explore.

Tissue were unavailable for some patients post 1L Osimertinib and blood samples show high potential as an alternative sample [11]. ddPCR is as an alternative technique with high sensitivity and specificity for MET amplification testing and it has been explored in previous study[12]. Besides, ddPCR blood assay for MET amplification testing still need be further validated through concordance of MET amplification between FISH testing in tissue and ddPCR testing in plasma.

This real-world, multi-center study will elucidate the gene profile post Osimertinib 1L treatment in tissue and plasma and will also help to guide the following treatment.

## 2.2 Background

While similar to 1/2 G EGFR-TKI, acquired resistance to Osimertinib invariably often develops with a median PFS of 19 months[1]. The characterization of the landscape of resistance enables the development of subsequent therapies, but mechanisms of resistance to Osimertinib is primarily derived from patients who received Osimertinib after other EGFR-TKIs, such as *EGFR C797*, *EGFR G724*, *EGFR L792*, *MET* amplification, and so on[2-5]. Besides, *MET* overexpression is also a key resistance mechanism after 1L Osimertinib failure[8]and the prevalence data of *MET* amplification by FISH testing (gold standard testing method for *MET* amplification) and *MET* overexpression by *MET* IHC testing in Chinese advanced EGFRm NSCLC patients who had disease progression following 1L osimertinib are very limited. The mechanisms of resistance to Osimertinib in the first-line treatment are far from being clearly explored. As Osimertinib in the first-line treatment is applied more and more widely in advanced EGFRm+ NSCLC patients, we urgently need to know the resistance mechanisms to guide subsequent treatment strategy. Until now, the largest study to explore acquired resistance mechanism to 1L Osimertinib was FLAURA study, which detected 91 paired plasma samples by next generation sequencing (NGS) . The most common acquired resistance mechanisms were *MET* amplification (15%) and *EGFR C797X* mutation (7%)[6]. The result was quite different from the study conducted by Adam J. Schoenfeld et al using tissue (N=27), with squamous transformation accounting for 15% and *MET* amplification 7%[7]. The reason for different

results maybe because these two studies used different samples to analyse resistance mechanisms, and the above two detection methods may have different sensitivity and specificity. In addition, Schoenfeld et al study was limited to patients at one site, Memorial Sloan Kettering Cancer Center in NY, USA.

Currently, analysis of circulating tumor DNA(ctDNA) has been the predominant method to investigate acquired resistance mechanisms, but non-genetic mechanisms of resistance, including histologic transformation and protein expression change cannot be captured by plasma NGS analysis. Compared to tissue analysis, sensitivity for copy number changes and chromosomal rearrangements using plasma samples is instable[3, 4, 19-23]. ddPCR is as technique with high sensitivity and specificity, which is widely used for the absolute quantification of nucleic acid through Poisson distribution [24] and also as an alternative technique for MET amplification testing in plasma samples has been explored in some previous studies. Kitazono et al. have attempted to use ddPCR to detect MET amplification in three blood samples of NSCLC patients with EGFR-TKI resistance and proved its feasibility at the first time [25]. The recent study further explored the performance of MET amplification testing by ddPCR in tissues and paired peripheral blood samples from advanced NSCLC patients who had progressed on EGFR-TKI[26]. A total of tissues and the paired peripheral blood samples from 103 advanced NSCLC patients who had progressed on EGFR-TKI were collected for MET amplification testing by using ddPCR. In parallel, MET amplification was verified by FISH in tissue samples. The concordance rate of MET amplification in tissue samples between ddPCR and FISH was 100% (102/102), and it was 94.17% (97/103) by ddPCR testing between tissue and paired and peripheral blood samples with performance of sensitivity 66.67% and specificity 98.86%. Therefore, ddPCR is an potentially alternative method for MET amplification testing in both tissues and peripheral blood samples, which is worthy of exploring and validating in more studies (appendix H).

Thus, this study plans to use paired tumor tissue and whole blood to detect molecular and histologic mechanisms of resistance to 1L Osimertinib and to assess the concordance of plasma and tissue. And these paired tissue and blood samples are also used to assess the concordance of MET amplification between FISH and ddPCR testing as exploratory endpoints. Additional, the prevalence of MET amplification by FISH testing and MET overexpression by IHC testing, and the overlap ratio of prevalence between MET amplification and MET overexpression are also as exploratory endpoints in this study.

## **2.3      Benefit/Risk Assessment**

### **2.3.1      Risk Assessment**

This is a real-world study, which will not affect or interfere with patients' routine medical

diagnosis and treatment, so it will not increase other related risks.

### **2.3.2 Benefit Assessment**

The results of the research may not be directly used for patients' diagnosis and treatment, but the analysis of gene profile after Osimertinib 1L treatment will eventually help oncologists to make more effective treatment strategies in the future.

### **2.3.3 Overall Benefit: Risk Conclusion**

Based on a review of the potential benefits and risks, it is considered to be reasonable and appropriate to investigate gene profile in *EGFR*m advanced NSCLC patients post Osimertinib 1L treatment failure

### 3 OBJECTIVES AND ENDPOINTS

**Table 2 Objectives and Endpoints**

Objectives	Endpoints
Primary	
To describe the gene profile in EGFR m advanced NSCLC patients post Osimertinib 1L treatment.	
 
Gene profile in tissue Gene profile defined as gene alternation detected by NGS and frequency of every gene alternation. All gene alterations include gene mutation, CNV, fusion, etc. The frequency of all gene alteration detected by NGS(%) = (number of patients with every gene alteration detected by NGS)/(total number of patients in the FAS)×100%.
 

Secondary	
To assess the concordance of plasma and tissue	
 
Gene profile in plasma Gene profile defined as gene alternation detected by NGS and frequency of every gene alternation.
 
Concordance of plasma and tissue Using selected representative genes (for example EGFR, MET, PIK3CA and etc.) to measure the concordance. Concordance of Gene X in plasma and tissue is defined as sensitivity, specificity, positive predictive value (PPV) and negative predictive value (NPV) between plasma and tissue results., Tissue sample is the reference standard.                     
 
sensitivity=(number of patients with positive result in both plasma and tissue)/(total number of patients with positive result in tissue samples)×100%;
 
specificity=(number of patients with negative result in both plasma and tissue)/(total number of patients with negative result in tissue samples)×100%.
 
PPV (%)=(number of patients with positive result in both plasma and tissue)/(total number of patients with positive result in plasma samples)×100%;
 
NPV (%)=(number of patients with negative result in both plasma and tissue)/(total number of patients with negative result in plasma samples)×100%
 
 
 
The percentage of pathology transformation Pathology transformation is defined as those transformation from non-small-cell lung cancer to small-cell lung cancer or from adenocarcinoma to squamous carcinoma, can be observed by IHC
 

CCI	

The figure consists of two side-by-side bar charts, both titled 'CCI'. The left chart has a single data series represented by a series of black bars of varying lengths. The right chart has multiple data series, each represented by a different pattern of black bars. The bars are grouped by category, indicated by small black squares preceding the bar groups.

## 4 STUDY DESIGN

### 4.1 Overall Design

This is a real-world, multi-center prospective study elucidating the gene profile in common *EGFR*m (ex19del and L858R) locally advanced or metastatic NSCLC patients post Osimertinib 1L treatment. The main assumption is that gene profile in tissue and plasma could further guide the following treatment strategy.

Approximately 200 participants in *EGFR*m locally advanced or metastatic NSCLC with the evidence of disease progression following 1L Osimertinib will be enrolled.

Participants will be required to provide paired tissue and whole blood after disease progression following 1L Osimertinib. 200 tissue samples and 200 whole blood samples will be used to detect gene alteration by NGS, respectively. 200 tissue samples will be used to detect pathological transformation by IHC. The sample size of MET amplification testing by FISH and MET overexpression by MET IHC in tissue samples is approximately 80-100 respectively. The sample size for MET amplification testing by ddPCR in blood samples is the same.

Baseline information consists of demography, smoking history, physical examination, medical history, ECOG/WHO performance status, *EGFR* mutation type, histology, clinical stage with lymph node and distant metastasis at diagnosis and post 1L Osimertinib, duration of 1L Osimertinib treatment, best response of 1L Osimertinib and progression pattern post 1L Osimertinib.

### 4.2 Scientific Rationale for Study Design

#### 4.2.1 Rationale for primary, secondary and exploratory endpoint

The primary objective is to describe the gene profile in tissue in *EGFR*m locally advanced or metastatic NSCLC patients post on 1L Osimertinib failure, which could help clinicians provide the following treatment strategy.

The secondary objective is to describe the gene profile in plasma, to assess the concordance of plasma and tissue, and the percentage of pathology transformation. Gene profile in plasma and the percentage of pathology transformation will be detected and analysed by NGS and IHC, respectively. Concordance of plasma and tissue is to explore whether plasma can be substitute for tissue when patients cannot accept tissue biopsy, which is defined as sensitivity, specificity, PPV and NPV of representative genes. According to the assay performance, sensitivity 80% is acceptable. If the point estimate for sensitivity is  $\geq 80\%$ , plasma samples are supposed to be consistent with tissue sample for NGS testing.

In the case of sufficient tissue samples, the exploratory endpoints is further to assess prevalence of MET amplification by FISH in tissue samples, the concordance of MET amplification

between FISH testing in tissue samples and ddPCR testing in blood samples, the prevalence of MET overexpression by MET IHC testing and the overlap ratio of prevalence between MET amplification by FISH and MET overexpression by MET IHC. The prevalence data of MET overexpression by MET IHC and MET amplification by FISH in post 1L Osimertinib resistance patients in China are very limited.

Tissue were unavailable for some patients post 1L Osimertinib and ddPCR testing will offer alternative method for MET amplification testing in blood samples. Concordance of MET amplification testing between ddPCR in plasma samples and FISH in tissue samples is to explore whether plasma can be substitute for tissue when patients cannot accept tissue biopsy, which is defined as sensitivity, specificity, PPV and NPV of representative genes.

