### **Number of Participants:**

Approximately 200 participants in *EGFR*m locally advanced or metastatic NSCLC with the evidence of disease progression following 1L Osimertinib will be enrolled and 15 sites will be involved to elucidate the gene profile in paired tissue and plasma so that approximately 180 participants whom would be get gene profile, assuming a 10% drop-out.

**Note:** "Enrolled" means a participant's, or their legally acceptable representative's, agreement to participate in a clinical study following completion of the informed consent process. Potential participants who are screened for the purpose of determining eligibility for the study, but are not randomly assigned/assigned in the study, are considered "screen failures", unless otherwise specified by the protocol.

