##### **8.3.2.2.2 Concordance of plasma and tissue**

Using selected representative genes (for example *EGFR*, MET, PIK3CA and etc.) to measure the concordance. Concordance of Gene X in plasma and tissue is defined as sensitivity,

[figure not shown]
specificity, positive predictive value (PPV) and negative predictive value (NPV) between plasma and tissue results. Tissue sample is the reference standard. The 95% confidence intervals using Pearson-Clopper method will be provided.

- sensitivity=(number of patients with positive result in both plasma and tissue)/(total number of patients with positive result in tissue samples)×100%;
- specificity=(number of patients with negative result in both plasma and tissue)/(total number of patients with negative result in tissue samples)×100%.
- PPV (%)=(number of patients with positive result in both plasma and tissue)/(total number of patients with positive result in plasma samples)×100%;
- NPV (%)=(number of patients with negative result in both plasma and tissue)/(total number of patients with negative result in plasma samples)×100%

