4.2.3 Secondary outcome(s)

Gene profile in plasma

Gene profile is defined as gene alteration detected by NGS and frequency of every gene alteration.

[figure not shown]
Proportion of Gene X alteration(%) = (number of patients with Gene X alteration, which is an example of a certain gene)/(total number of patients in the FAS)×100%.

Concordance of plasma and tissue

Using selected representative genes (for example EGFR, MET, PIK3CA and etc.) to measure the concordance of plasma and tissue mutation for each gene. Concordance of Gene X in plasma and tissue is defined as sensitivity, specificity, positive predictive value (PPV) and negative predictive value (NPV) between plasma and tissue results.

The percentage of pathology transformation

Pathology transformation is defined as those transformation from non-small-cell lung cancer to small-cell lung cancer or from adenocarcinoma to squamous carcinoma, can be observed by IHC.

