5.4.2 Secondary Endpoint

The secondary objective is to assess gene profile in plasma, concordance of plasma and tissue and the percentage of pathology transformation will be analysed by NGS method and IHC. All gene alterations in plasma(e.g., gene mutation, amplification, deletion, fusion, etc.) detected will be observed. Proportion of Gene X alteration(%) = (number of patients with Gene X alteration, which is an example of a certain gene)/(total number of patients in the FAS)×100%. Some cases which patients have more than one gene alteration need to be considered, therefore percentages may not add up to 100%.

Using selected representative genes to measure the concordance. The representative genes should include the top 20 mutated genes observed in tissue samples. Concordance of Gene X in plasma and tissue is defined as sensitivity, specificity, positive predictive value (PPV), negative predictive value (NPV), and overall percent agreement between plasma and tissue results., Tissue sample is the reference standard.

Sensitivity=(number of patients with positive result in both plasma and tissue)/(total number of patients with positive result in tissue samples)×100%;

Specificity=(number of patients with negative result in both plasma and tissue)/(total number of patients with negative result in tissue samples)×100%.

[figure not shown]
PPV (%)=(number of patients with positive result in both plasma and tissue)/(total number of patients with positive result in plasma samples)×100%;

NPV (%)=(number of patients with negative result in both plasma and tissue)/(total number of patients with negative result in plasma samples)×100%.

Overall percent agreement(%) =(number of patients with same result <positive or negative> in both plasma and tissue)/(total number of patients in FAS)×100%

Pathology transformation defines as pathological type of lung cancer change, which will be confirmed by pathologists. Number and percentage of patients with pathology transformation will be summarized. Proportion of pathology transformation(%) = (number of patients with pathology transformation)/(total number of patients in the FAS)×100%.

CCI

CCI

[REDACTED]

[REDACTED]
[REDACTED]
[REDACTED]

[REDACTED]

[figure not shown]
		[REDACTED] [REDACTED]	[REDACTED]	
[REDACTED]	[REDACTED]			
	[REDACTED]			
[REDACTED]				

[REDACTED]
[REDACTED]
[REDACTED]
[REDACTED]
[REDACTED]
[REDACTED]

[REDACTED]
[REDACTED]
[REDACTED]
[REDACTED]
[REDACTED]
[REDACTED]
[REDACTED]
[REDACTED]

CCI

CCI

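### Protocol 4.2.1 calls plasma consistent with tissue on a sensitivity point estimate of 80% alone, without using the planned exact CI, specificity, PPV or NPV, and without saying how per-gene results support a general statement about plasma

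*Protocol*

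**What the plan says.** Protocol 4.2.1 gives the purpose of the concordance analysis: to explore whether plasma could stand in for tissue when a patient cannot have a biopsy. Concordance is a four-part measure, "which is defined as sensitivity, specificity, PPV and NPV of representative genes". The section then takes 80% sensitivity as acceptable, citing assay performance, and states a verdict. The condition begins "If the point estimate for sensitivity is" and is met at 80% or more; the conclusion is that "plasma samples are supposed to be consistent with tissue sample for NGS testing".

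The analysis sections are fuller:

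- Protocol 8.3.2.2.2 defines all four measures for a Gene X, with tissue as the reference, and adds: "The 95% confidence intervals using Pearson-Clopper method will be provided".
- SAP 4.2.3 sets the unit. Representative genes are used "to measure the concordance of plasma and tissue mutation for each gene".
- SAP 5.4.2 says "The representative genes should include the top 20 mutated genes observed in tissue samples" and adds overall percent agreement.

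The 80% sentence appears only in protocol 4.2.1. Protocol section 8 and the visible SAP text neither repeat it nor withdraw it. The SAP's list of changes to protocol planned analyses names only the added overall percent agreement.

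**The concern.** The definition and the verdict do not match. Four measures define concordance, but one of them, as a bare estimate, decides whether plasma is called consistent. Two things follow.

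First, the number of tissue-positive patients for a gene may be small, so an estimate of 80% can be compatible with much lower sensitivity. The verdict does not look at the interval that would show this. Nor does it look at specificity or PPV, although a false-positive plasma call also matters when plasma replaces tissue.

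Second, sensitivity is calculated gene by gene, but the conclusion is about plasma samples in general. The sentence does not say whether one gene, most genes or every gene must reach 80%. The protocol expects alterations to differ: its section 2.2 says that, compared with tissue, "sensitivity for copy number changes and chromosomal rearrangements using plasma samples is instable". One gene's result therefore cannot speak for the others.

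At stake is a published statement that plasma can substitute for tissue which the data for that gene, or for other genes, would not support. The SAP's timing section has the interim analysis cover the secondary outcomes, so such a statement could also be made on about half the patients.

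**Working it through.** **The plan's own figures.** Protocol 8.1 gives an exact 95% CI of 14.7–26.2% for a 20% incidence in 200 patients. Clopper-Pearson limits for 40/200 reproduce this, as they do the other four rows of the table. The chance of at least one case at 1% incidence is 1 − 0.99^200 = 86.6% (stated as 86%). Neither document gives a precision figure for sensitivity, whose denominator is the tissue-positives and not all patients.

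**Inputs**

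- Evaluable patients: 180. The synopsis expects "approximately 180 participants whom would be get gene profile" after 10% drop-out (200 × 0.9).
- Tissue-positives per gene, n: assumptions, taken as incidence × 180.
  - 7% gives 13 (12.6 rounded up). This is the MET amplification rate in the single-centre tissue study cited in the synopsis rationale.
  - 10% gives 18, the lowest incidence in the 8.1 table.
  - 20% gives 36, the planning incidence.
  - 100% gives 180, the upper extreme.
- Pass: x/n ≥ 0.80, so the lowest passing x is 0.8n rounded up.

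**Formulas.** The lower limit is the 2.5% quantile of Beta(x, n − x + 1) and the upper limit is the 97.5% quantile of Beta(x + 1, n − x). The chance of passing is P(X ≥ lowest passing x), with X binomial(n, true sensitivity).

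| n | Lowest pass | Exact 95% CI | Pass if true 60% | true 70% | true 75% | true 80% |
|---|---|---|---|---|---|---|
| 13 | 11/13 = 84.6% | 54.6–98.1% | 5.8% | 20% | 33% | 50% |
| 18 | 15/18 = 83.3% | 58.6–96.4% | 3.3% | 16% | 31% | 50% |
| 36 | 29/36 = 80.6% | 64.0–91.8% | 0.7% | 11% | 29% | 57% |
| 180 | 144/180 = 80.0% | 73.4–85.6% | about 0% | 0.2% | 7% | 54% |

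**Interim.** With about 100 patients and an assumed 10 tissue-positives, 8/10 passes with a CI of 44.4–97.5%. A true 70% then passes 38% of the time and a true 60% passes 17%.

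**Specificity.** The verdict sets no limit on it. PPV = (sens × p) / (sens × p + (1 − spec)(1 − p)). With sensitivity 80%, p = 10% and an assumed specificity of 95%: 0.08 / (0.08 + 0.05 × 0.90) = 0.08 / 0.125 = 64%. About one plasma-positive call in three would then be unconfirmed in tissue, and the verdict would still be that plasma is consistent.

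**The case against.** The strongest reply is that the sentence is not an operative rule. It occurs once, in softly worded rationale text. It is absent from the endpoint tables, from protocol section 8 and from the visible SAP. No hypothesis test, sample size or treatment decision depends on it, and the aim is exploratory. All of that stands, and it limits the severity. It does not remove the point: the sentence is a pre-stated numeric criterion with a conclusion attached, and nothing visible replaces it.

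A second reply is that a true 75% passing about 30% of the time is ordinary sampling variation five points below a descriptive benchmark, and the planned CI would show it. That is fair for the reporting. The verdict, however, does not require anyone to look at the CI.

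Three stronger readings are tempting but are not supported:

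- A reader might infer that the plan neglects uncertainty and the other measures altogether. It does not: all four measures are planned, and protocol 8.3.2.2.2 gives them exact CIs.
- A reader might infer that sensitivity could be pooled over genes, so that EGFR carries weakly detected genes. No pooled sensitivity is defined. The formula counts patients for one Gene X, and SAP 4.2.3 confirms the unit. The open question is only how per-gene results become a general statement.
- A reader might take the 66.67% blood sensitivity in protocol 2.2 as a realistic true value for MET amplification. Appendix H Table B shows amplification found in blood in 4 of 9 tissue-positives (44.4%); 66.67% arises only if polysomy also counts as positive, (4 + 6)/(9 + 6). The assay is ddPCR, not NGS. Likewise, the 15% MET amplification rate in the rationale comes from plasma, so it is not used here as a tissue count.

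**Conclusion.** The concern holds for the verdict sentence in protocol 4.2.1 and no further. As written, it lets plasma be called consistent with tissue when the lower confidence limit for a gene is between about 55% and 64% (13 to 36 tissue-positives), at any specificity, and without saying which genes the statement covers.

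The realistic error at the final analysis is passing a true sensitivity of 70–75%: 11–20% of the time at 70%, and 29–33% at 75%, for 13 to 36 tissue-positives. A true 60% passes 6% of the time or less. For an alteration present in nearly every patient, such as gene-level EGFR, the problem is small. The top-20 rule in SAP 5.4.2 favours genes with more positives but guarantees no minimum count.

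These figures rest on 180 evaluable patients and assumed tissue-positive counts; the PPV figure rests on an assumed specificity. Severity is minor to moderate: the reporting is sound, and only the step from estimate to conclusion needs correcting.

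**What to change.** Add to SAP 5.4.2, and to protocol 4.2.1 at the next amendment if there is one:

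> The 80% sensitivity figure is a per-gene descriptive benchmark, read together with its two-sided 95% Clopper-Pearson CI, the number of tissue-positives, and specificity, PPV and NPV with their CIs. No conclusion that plasma is consistent with, or can substitute for, tissue will be drawn from the sensitivity point estimate alone, at the interim or final analysis, and any such statement will be limited to the named gene.

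Record the departure from protocol 4.2.1 in the SAP's list of changes to protocol planned analyses.

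The cost is wording; the intervals and measures are already planned. A separate protocol amendment, which under Appendix A 1 would need ethics and regulatory approval, is not warranted for this alone. A CI floor is not needed either: requiring a lower limit of at least 80% would demand 18/18 or 34/36 and could not be met with 13 positives. The downside is that fewer genes, mainly those with few tissue-positives, will support a substitution statement.
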